### Homeostasis model of assessment (HOMA):

*Insulin Resistance HOMA-IR* = glucose [mmol/L] x insulin [mU/L] / 22.5 (166, 167). Patients with insulin resistance (HOMA-IR >2.73) (129) and healthy donors with HOMA-IR  $\leq$ 2.73 are eligible.

Serum metabolomics: Serum will be thawed and ultra-filtered for removal of large molecular weight proteins and lipoproteins. The metabolomics analysis by nuclear magnetic resonance spectroscopy is performed as described above for stool samples.

### 1.6.4 Nutritional and other assessment

Anthropometry: Weight, BMI, waist circumference and waist to hip ratio are measured. Change in these parameters and excess weight loss (in %) between baseline and 1 month as well as between baseline and 3 months post FMT will also be assessed.

*Food intake:* Three-day food records will be kept. Participants will eat their regular meals and itemize the food using the 2D Food Portion Visual chart (Nutrition Consulting Enterprises, Framingham, MA) to estimate portion sizes. The data will be analyzed using Food Processor SQL (ESHA Research) to assess the intake of macro- and micronutrients (168, 169) (*food record form enclosed*).

*Physical activity:* Patients will record their physical activity (daily life activities and sports exercises) for seven days, including time, type and duration and intensity of these activities. Units of exercise will be calculated (1 unit = 30 min mild, 20 min moderate, 10 min strenuous, or 5 min very strenuous activity) (170) (*food/activity forms enclosed*).

Appetite will be assessed in a fasting state, using a validated tool in obese subjects (172, 173). Research participants will be asked to rate their level for each feeling on a 100 mm visual analogue scale, therefore participants will have a numerical ranking for each feeling in mm which can be used for statistical analysis (*see attached form*).

Blood pressure: will be measured in a seated position according to clinical practice.

# 1.6.5 Psychological assessment

At baseline to all participants and 1 and 3 months after FMT for patients, we will also administer: *The Montgomery-Åsberg Depression Rating Scale (MADRS)*, a 10-item questionnaire which psychiatrists use to measure the severity of depressive episodes in patients with mood disorders (174); and *The Hamilton Anxiety Rating Scale (Ham-A)*, a clinician-rated evaluation whose purpose is to analyze the severity of anxiety. The scale is intended for adults, adolescents, and children and should take approximately ten to fifteen minutes to administer (175). Both questionnaires will be administered by the study coordinator.

To identify whether there are particular personality styles that make someone a good donor, we will also administer to the donors at baseline: the *Connor-Davidson Resilience scale (CD-RISC)*, which comprises of 25 items, each rated on a 5-point scale (0-4), with higher scores reflecting greater resilience (176).

*Quality of life:* This will be assessed using the RAND 36-Item Health Survey 1.0 (RAND SF-36), which has been developed for the Medical Outcomes Study (177). Patients will fill out the form at baseline and 3 months after FMT (*all psychiatric forms enclosed*).

### **1.7 Statistical Considerations**

### 5.7.1 Sample size and power calculations

Our sample size is determined based on current literature, feasibility and the experience of team members, due to the pilot nature of the proposed study. Following common practice for this kind of studies (e.g. (179, 180)), we plan to recruit until we have randomized 36 eligible patients (18 per FMT

group). With a 20% attrition rate we assume that 15 patients per group will finish the intervention. This represents a greater sample size than the only previous FMT study on metabolic syndrome (26). We are confident that this sample size will allow us to investigate the stated aims.

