# **1 MATERIAL AND METHODS**

#### 1.1 Study Design

This will be a double-blind, placebo controlled randomized controlled trial. Morbidly obese men and women with IR who are eligible for bariatric surgery but did not perform such procedure will be approached. Those consenting will be randomly assigned to either allogenic FMT (prepared from stool donated by healthy lean donors with BMI <23 kg/m^2, matched for gender with the recipient) or autologous FMT (re-infusion of own collected feces; placebo). We plan to randomize 30 patients. Stool, blood, anthropometric measurements, questionnaires, quality of life, depression and anxiety will be assessed and will be collected before FMT and at 1 and 3 months post FMT. At baseline a physical examination will be performed, and will also be preformed if symptoms are present 3-months post-FMT . OM will be assessed before FMT and 3-months post FMT. Intestinal mucosa biopsies will be collected during colonoscopy for FMT administration as well as samples for safety.

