### 5.8 Randomization and blinding

# 5.8.1 Randomization list and blinding

Allocation concealment will be maintained by the lab technologist at the UHN-SHS FMT program, who will prepare the fecal filtrates for each patient but will otherwise not be involved in the conduct or analysis of the study. The allocation list will be kept in sequentially numbered envelopes with the group assignments. The group assignments will be based on a blocked randomization list (4 patients per block), created in SAS proc PLAN. The list will be created to randomize 60 patients, even though 36 are planned to be randomized. As we are including only dosed patients in the analysis, this will allow us to randomize additional patients, in case the FMT is not conducted in participants after they were randomized. The list is created by a person at the UHN, who will not be involved in conduct or analysis of the study. The technologist will have to date and sign the opened envelope.

The technologist will open the allocation on the day the patients at providing their baseline stool sample. Only if the patient is allocated to autologous FMT, a fecal filtrate from the patient's own feces is produced. On the day of the FMT, the bags with the fecal filtrate will be provided to the study team

without indication, which type of FMT is provided. Only the patient number will be on the label. Both the patient and the study team (clinical team, study coordinator, data analyst) will be blinded to group assignments.

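### The sample-size figures disagree: 30 versus 36 randomized, and 18 per group at 20% attrition gives about 14 completers per group, not 15

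*Combined protocol and SAP*

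**What the plan says.** Three sections of the combined protocol and SAP give the trial's size.

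- Section 1.1 (Study Design): "We plan to randomize 30 patients".
- Section 5.7.1 (Sample size and power calculations): "we plan to recruit until we have randomized 36 eligible patients", with 18 in each FMT group. It continues: "With a 20% attrition rate we assume that 15 patients per group will finish the intervention".
- Section 5.8.1 (Randomization list and blinding): "The list will be created to randomize 60 patients, even though 36 are planned to be randomized". The list uses blocks of four. The spare places are for patients added when someone already randomized does not receive the FMT.

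Section 5.7.1 gives no effect size, standard deviation or power. It explains the size this way: "Our sample size is determined based on current literature, feasibility and the experience of team members, due to the pilot nature of the proposed study". After the completer figure it says that the size exceeds that of one earlier FMT study in metabolic syndrome, and ends: "We are confident that this sample size will allow us to investigate the stated aims".

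Two other places bear on the count. The withdrawal criteria in Section 1.3.1 say that patients who cannot be given the FMT are withdrawn, replaced by further randomizations, and not followed up. Section 5.7.3 analyses all dosed patients first and a per-protocol set second.

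**The concern.** A reader who wants to know how many patients will be randomized finds two answers, 30 and 36. A reader who wants to know how many are expected to finish finds 15 per group, which the stated 18 and 20% do not give.

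The number randomized is the figure against which recruitment is judged complete, so it should have one value. The completer figure matters less. It is still part of the only quantitative support that Section 5.7.1 offers for its size, so it should follow from the numbers beside it.

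**Working it through.** **Inputs.** 30 randomized (Section 1.1). 36 randomized, 18 per group, 20% attrition and 15 completers per group (Section 5.7.1). 36 planned, in blocks of four (Section 5.8.1). The treatment is a single dose, so I read finishing as completing the 3-month follow-up.

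**1. The plan's 15.** Applying the attrition to those randomized:

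- per group: 18 × (1 − 0.20) = 14.4
- in total: 36 × 0.80 = 28.8, against a stated 2 × 15 = 30

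The loss that takes 18 to 15 is 1 − 15/18 = 16.7%. The stated pair fits exactly if 15 was inflated by adding 20%: 15 × 1.20 = 18. That is a likely source, though the document does not say so. To expect 15 completers after a 20% loss, the divisor is 0.80: 15/0.80 = 18.75, so 19 per group and 38 in total.

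**2. 30 against 36.** At 20% attrition:

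| Randomized | Completers in total | Completers per group |
|---|---|---|
| 30 (Section 1.1) | 30 × 0.80 = 24 | 12 |
| 36 (Sections 5.7.1 and 5.8.1) | 36 × 0.80 = 28.8 | 14.4 |

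The figure of 30 equals 2 × 15, so Section 1.1 may be giving the expected completers under the word for randomized. The documents do not confirm this. The block size fits 36 better: 36/4 = 9 full blocks, which gives 18 per group, whereas 30/4 = 7.5 blocks.

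**3. Effect on precision.** For a difference between two equal groups, the width of a confidence interval varies as 1/√n.

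- 14.4 against 15: √(15/14.4) = 1.021, about 2% wider
- 14 against 15: √(15/14) = 1.035, about 3.5% wider
- 12 against 14.4: √(14.4/12) = 1.095, about 9.5% wider

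**4. Effect on the detectable difference.** The plan states no power, so 80% is my assumption. With a two-sided 5% level and the normal approximation, the detectable standardized difference is (1.960 + 0.842) × √(2/n):

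| Completers per group | Detectable difference (SD) |
|---|---|
| 15 | 1.02 |
| 14.4 | 1.04 |
| 14 | 1.06 |
| 12 | 1.14 |

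**The case against.** **The completer gap is under one patient per group, and nothing is computed from it.** This stands. The gap is 0.6 per group and 1.2 in total. The size is justified by feasibility and the pilot purpose, so no power or precision figure has to be redone.

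**The initial analysis does not depend on completers.** This also stands. Section 5.7.3 takes all dosed patients first. The mixed models in Section 5.7.2 can use 1-month data from someone who misses month 3.

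**Replacement could deliver 15.** This stands in part. Section 5.7.1 does not say when the 20% is lost. As an illustration, suppose 4% are undosed and replaced and 16.7% are lost after dosing. Total loss is then 1 − 0.96 × 0.833 = 20%, and 18 dosed per group yield 15. But 18 dosed would need 18/0.96 = 18.75 randomized per group, so the number randomized would pass 36. If all the loss comes after dosing, replacement does not help and 14.4 stands. From 36 randomized at 20% loss, neither reading gives 15. It would be wrong, though, to assert that the 20% can only mean loss after dosing.

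**A stronger reading that should be resisted.** A reader might infer that the trial rests on an inflated size or is underpowered because of this slip. The documents do not support that. They set no power target, and the phrase about the size being sufficient can equally refer to the 36 randomized. The size of the earlier study is not given, so the comparison with it cannot be shown to fail.

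A reader might also note that, with independent 20% losses, a group of 18 reaches 15 completers with probability 0.50, and both groups do so with probability 0.25. That treats 15 as a threshold, which the plan never sets. By the same measure even 19 per group would give only 0.67 and 0.45.

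**Conclusion.** The sample-size figures are inconsistent as written, in two respects. The conflict between 30 and 36 randomized is the more important: a difference of six patients, or 12 against 14.4 completers per group at the stated attrition. The step from 18 to 15 is a small arithmetic slip. The stated inputs give 14.4, about 14 per group and 28–29 in total, and the cost in precision is 2% to 3.5%.

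The completer counts assume that the 20% applies to all patients randomized, equally in both groups. The precision figures compare completers only. The initial analysis of all dosed patients would be affected less by the second gap, or not at all. This is a matter of correct and consistent statement. It does not show that the trial cannot meet its aims.

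**What to change.** 1. In Section 1.1, change the number to be randomized to 36 (18 per group), in line with Sections 5.7.1 and 5.8.1.
2. In Section 5.7.1, state that 20% attrition from 18 per group leaves about 14 completers per group (28–29 in total).
3. In the same place, say whether the 20% includes patients who are randomized but not dosed and are replaced under Section 1.3.1, and whether the 36 counts those patients.

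Lowering the stated attrition to 17% so that 15 comes out is not recommended. Nothing in the documents supports that rate over 20%, and it would only fit the assumption to the answer.

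The cost is wording only. Recruitment, the randomization list and the analysis stay as they are. The stated completer figure becomes slightly less favourable.

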### 5.7.2 Statistical analysis plans

A descriptive summary of all measurements will first be compiled using appropriate graphical representations, and means, standard deviations and proportions will be calculated. Baseline characteristics of the randomized groups will be compared to ensure balance on the important variables (e.g. HOMA, BMI). Trajectory plots will be created to examine visually the changes over time.

The changes in the outcome variables of (HOMA-IR, weight, scores for appetite, quality of life, anxiety, and depression) within the two FTM groups (allogenic vs. autologous) will be compared using generalized linear mixed models (GLMM), where the within and between groups changes over time will be examined simultaneously. Factors with known influence on the outcomes will be examined for possible inclusion in our multivariate models as covariates, particularly if found imbalanced between the randomized groups. For patient drop-out, we will check missingness patterns and employ appropriate methods of handling missing data (181). The relationships between changes in outcomes and IM will first be investigated using correlation analysis (Spearman and Pearson correlation coefficients, Chi-square and Fischer exact tests as appropriate), and subsequently using methods for correlated data when considering multiple measures (incl. covariates, multiple time points, etc.). For the latter, we will employ generalized linear and nonlinear mixed models, as well as the generalized estimating equations approach. Goodness-of-fit tests will be applied for model diagnostics (182). In addition, principal component analysis (183), co-inertia analysis will be considered when investigating possible strategies for dimension reduction (where large numbers of variables may be correlated).

Statistical analyses will be performed using SAS 9.4 and R 3.2 (or subsequent versions as they become available), and all tests will be two-sided with a significance level of 5%. Where necessary, p-value adjustments for multiple testing (e.g. Holm's Bonferroni Step-down, Benjamini and Hochberg False Discovery Rate) will be employed (184).

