### **1.3 Study Participants**

#### 1.3.1 Patients receiving intervention

Inclusion criteria: Morbidly obese men and women, age 18 years or older, fulfilling the 1991 NIH criteria (BMI >40 kg/m^2 or BMI >35–40 kg/m^2 with other severe weight loss responsive comorbidities) (12, 36), who were referred to the Bariatric Clinic at the Toronto Western Hospital for weight loss surgery, but declining or deferring the surgery, will be included. Will accept also patients fulfilling same criteria above who are approaching us via other streams like MTOP website, cinicaltrials.gov and flyers posted in Hospitals and Universities. Patients have to be insulin resistant, which is defined as having a HOMA-IR value >2.73 (129).

*Exclusion criteria:* Regular intake of: non-steroidal anti-inflammatory drugs; immune-suppressed subjects for any reason (due to diseases or medications like steroids and other immune-suppressant agents); iron supplements; prebiotics or probiotics from other than food sources, antibiotics, or any experimental drug in the 3 months prior to study entry; type 1 or type 2 diabetes, severe chronic gastrointestinal diseases, previous gastrointestinal surgery modifying the anatomy, smoking; pregnancy or breastfeeding.

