Due to the control arm receiving autologous FMT, we are using frozen fecal filtrate. Patients need to prepare for FMT colonoscopy following standard instructions with clear fluids and a laxative the day before the procedure to clean the colon (*see colonoscopy preparation instructions*). The stool for FMT has to be collected before the adjustment of diet and bowel preparation in order to maintain the original IM (stool need to be collected no later than 3 to 4 days prior to colonoscopy). The use of an autologous FMT control group is essential, as the bowel preparation and colonoscopy itself can induce changes to the IM (134, 135). Lean donor stool will be processed the same way as the autologous stool. Freezing stool by adding glycerol as a cryoprotectant has been shown to yield active FMT preparations (136, 138). Costello and colleagues (133) examined the long-term stability of frozen stools for FMT and confirmed that fecal filtrate for treatment of *C. difficile* infection could safely be stored frozen in 10% glycerol for at least 6 months without loss of clinical efficacy or viability in the six bacterial groups tested. In our study, we will store fecal filtrate for a maximum of 3 months before using it for FMT.

We will follow patients for 3 months post FMT. Vrieze et al. found improvements in IR already 6 weeks after FMT, without weight loss (26). We will extend the observation period, as 6 weeks might not have been sufficient to cause significant weight loss. In addition, we want to see, whether FMT leads to sustainable improvements in IR and IM. Patients will be approached by the MTOP Team and will be offered a 3 years follow-up post-FMT (REB# 16-5404-AE, separate consent form).

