Morbidly obese patients: Patients will be approached if they have attended the information session and signed the psychosocial study consent where they agree to be contacted for future research studies. We will be targeting specifically those patients who decide not to go ahead with the bariatric surgery at this point in time (i.e. no follow-up arranged four weeks after the orientation session). Patients interested in our study calling us on their own initiative will be screened even if not previously evaluated by the Bariatric Clinic at TWH as long as they fulfil all other requirements. After a short phone screening, the patients receive a copy of the consent form, which will be discussed over the phone by the study coordinator. Then they will come to the hospital for the screening visit, where their medical history and medications are recorded and HOMA-IR will be measured to assess eligibility. Patients will be provided with forms for food records, activity log, environmental questionnaire, and a stool collection kit. If the patient lives far or specifically request it, he can have blood works done in an outside lab and kit will be mailed home. In this case medical history and medications are recorded over the phone. Once eligibility is confirmed depending on HOMA-IR measured at screening, patients will be called back for the baseline visit. The following will be assessed: bloodwork, anthropometric measurements, appetite rating, psychological MINI interview, depression, anxiety, and quality of life questionnaires. Then, an FMT appointment will be scheduled and patients will be randomized. Patients will collect stool samples adequate for a single transplant (150gr) before they start the bowel preparation for the colonoscopy. In the week before the stool sample is collected, they will complete the questionnaires provided at baseline. When they bring their stool sample to the hospital, completed forms will be collected, anthropometric measurements will be performed. Baseline measurements will be repeated at 1 and 3 months post FMT, except for quality of life, depression and anxiety scores.. After FMT patients are required to fill-in a symptoms diary to keep track of any AE possibly occurring. In addition, during the colonoscopy performed to administer FMT, mucosal samples will be taken from the rectum, the colon, and the terminal ileum to assess the mucosa-associated microbiome. Blood and colon secretions will be collected to evaluate the baseline immune status of the subject (infections existing prior to FMT) and colon secretions will be also stored for future research.

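### Section 5.7.2 does not commit to baseline HOMA-IR in the main between-arm model, which can cost precision at about 15 patients per arm

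*Combined protocol and SAP*

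**What the plan says.** HOMA-IR is the main outcome (section 1.2). Blood is taken before FMT and at 1 and 3 months (section 1.1). Under section 5.7.2, changes in HOMA-IR and the secondary outcomes in the two arms "will be compared using generalized linear mixed models (GLMM), where the within and between groups changes over time will be examined simultaneously".

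Baseline HOMA appears in that section only in a balance check: "Baseline characteristics of the randomized groups will be compared to ensure balance on the important variables (e.g. HOMA, BMI"). On covariates it says: "Factors with known influence on the outcomes will be examined for possible inclusion in our multivariate models as covariates, particularly if found imbalanced". Nothing commits the analyst to baseline HOMA-IR as a covariate or to a common baseline mean for both arms. The section also states that "all tests will be two-sided with a significance level of 5" per cent.

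Section 5.7.1 presents the trial as a pilot with no power claim, and "we assume that 15 patients per group will finish the intervention". Entry requires HOMA-IR above 2.73 at screening (section 1.3.1). Section 1.5 then provides a separate pre-treatment measurement: "Once eligibility is confirmed depending on HOMA-IR measured at screening, patients will be called back for the baseline visit", with bloodwork at that visit.

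**The concern.** Whether a mixed model uses the baseline value efficiently depends on its parameterisation, which 5.7.2 leaves open. With baseline as a response and a free mean in each arm, complete data give a 3-month contrast identical to the two-sample comparison of change scores. With baseline as a covariate, or with the arms constrained to a common baseline mean, the contrast is close to analysis of covariance (ANCOVA). Two analysts could both follow 5.7.2 faithfully and report intervals of different width.

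Observed imbalance is also a poor trigger. The precision gain comes from how well baseline predicts follow-up, whether or not the arms happen to differ. A pilot of this size yields mainly an estimate and its interval, so the width of that interval is what is at stake.

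**Working it through.** **The plan's own figure.** Section 5.7.1 randomizes 18 per arm and allows 20% attrition. Forward, 18 × 0.8 = 14.4; backward, 15 × 1.2 = 18. The stated 15 completers per arm is reproduced to within one patient and is used below. No power can be reproduced, because the plan gives no effect or SD.

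**Assumptions (none is in the documents).** Log-scale SD 0.5 and a 33% reduction, so the effect is −ln(0.67)/0.5 = 0.80 SD. The correlation rho runs from 0.3 to 0.9. k is follow-up SD divided by baseline SD. Tests are two-sided at 5%.

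**Formulae.** With k = 1, the variance of the arm difference is proportional to 2(1 − rho) for change scores and to 1 − rho² for ANCOVA, so the ratio is (1 + rho)/2. Estimating the slope with N = 30 multiplies it by 1 + 1/(N − 4) = 1 + 1/26 = 1.038. In general the large-sample ratio is k²(1 − rho²)/(1 + k² − 2·rho·k).

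**Worked case, rho 0.5, k = 1.** Ratio 0.75 × 1.038 = 0.779. Change-score noncentrality is 0.80/(1.00 × √(2/15)) = 2.19 on 28 df, power 56%. For ANCOVA it is 0.80/(√0.779 × √(2/15)) = 2.48 on 27 df, power 67%. Matching ANCOVA with change scores would take 15/0.779 = 19.3 per arm.

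| rho (k = 1) | variance ratio, formula | ratio, simulated | power, change → ANCOVA | change-score n per arm to match |
|---|---|---|---|---|
| 0.3 | 0.675 | 0.680 | 43% → 59% | 22 |
| 0.5 | 0.779 | 0.778 | 56% → 67% | 19 |
| 0.7 | 0.883 | 0.878 | 78% → 83% | 17 |
| 0.8 | 0.935 | 0.937 | 92% → 93% | 16 |
| 0.9 | 0.987 | 0.984 | no gain | 15 |

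The mean 95% half-width on the log scale falls from 0.438 to 0.360, 0.371 to 0.327, 0.287 to 0.270 and 0.234 to 0.227 at rho 0.3 to 0.8, that is by 18%, 12%, 6% and 3%.

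**Unequal variances.** With k = 1.25, power moves from 46% to 49% (rho 0.5), 65% to 64% (0.7) and 81% to 79% (0.8). At rho 0.8, rho × k = 1, so the large-sample gain is zero and only the 4% slope cost remains. With k = 0.8 and rho 0.5, power goes from 63% to 85%.

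**Entry threshold.** If the screening cut at 2.73 is applied to an assumed population with median 3 to 5 and rho 0.5, the in-trial rho is 0.36 to 0.46, variance is 17–27% lower, and power goes from 56–59% to 67–70%.

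**The rule in the plan.** Section 5.7.2 describes neither always adjusting nor never adjusting, so two readings of its covariate rule were simulated at k = 1, each with an assumed p < 0.10 trigger.

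| rho | never | only if imbalanced | if baseline predicts change | always |
|---|---|---|---|---|
| 0.3 | 43% | 44% | 59% | 59% |
| 0.5 | 56% | 57% | 67% | 67% |
| 0.7 | 78% | 78–79% | 83% | 83% |

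Under the null, rejection was about 3.6–4.8% for the imbalance rule and 5.0–5.7% for the association rule.

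**The case against.** The strongest reply is that the table above compares never adjusting with always adjusting, and the plan says neither. Its leading criterion for covariates is known influence on the outcome; imbalance is an emphasis, not a condition. Baseline HOMA is an obvious candidate, and an analyst who includes it because it is prognostic loses essentially nothing. This stands: the tabulated gains are upper bounds, and the true loss under 5.7.2 lies between about zero and those figures.

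It is also fair that the analyst is blinded (section 5.8.1), that a balance check uses no outcome data, and that averaging three fasting samples (section 1.6.3) would tend to raise rho, where the gain shrinks.

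Three stronger readings are tempting but not supported.

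- **That the result would be biased.** It would not: an unadjusted change comparison is unbiased under randomization.
- **That the covariate wording inflates false positives.** Applied consistently, either reading stays near 5%. Simulated rates of about 11–14% need success at either visit plus a free choice of the better of the adjusted and unadjusted results, and the plan states no such rule.
- **That the trial has no designated contrast at all.** There is one main outcome and a stated between-arm comparison. The opening part of the document was not available for this review, and section 5.7.1 refers to aims that may name a visit.

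What the reply does not remove is that permitted adjustment is not prespecified adjustment, and that the one trigger 5.7.2 emphasizes is the one that recovers almost none of the gain.

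**Conclusion.** The point holds as an improvement in precision and prespecification. Section 5.7.2 leaves open whether baseline HOMA-IR enters the main model. If it enters only on observed imbalance, or as a response with free arm means, the contrast has about change-score precision. Always adjusting would then lower the variance by up to about 32%, 22%, 12% and 6% at rho 0.3, 0.5, 0.7 and 0.8, assuming 15 completers per arm and equal variances. The power figures also assume a log-SD of 0.5 and a 33% reduction. There is almost no gain at rho 0.9, and little or none if follow-up variance is clearly larger than baseline variance. The missing commitment is certain; the size of any loss is not.

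Secondary: the visible 5.7.2 names no visit for the main HOMA-IR contrast. Section 1.4.4 leans towards 3 months ("we want to see, whether FMT leads to sustainable improvements in IR and IM") without designating it.

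**What to change.** State in section 5.7.2 that:

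- Baseline-visit HOMA-IR, not the screening value used for entry, is always in the primary mixed model, whatever the balance check shows. It enters as a covariate with its visit interaction, or through a common baseline mean for both arms.
- Each secondary outcome is adjusted for its own baseline where one is measured.
- Any further covariates are chosen before unblinding, on prognostic grounds.
- Unless the document already does so elsewhere, one visit is named for the main contrast (3 months fits section 1.4.4) and the other is secondary. The analysis scale is fixed before unblinding; log HOMA-IR is a reasonable choice.

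The cost is wording and one or two model parameters, with no new data. If adjustment turns out not to help, the penalty at 15 per arm is at most about 4% in contrast variance, or about 1.5 power points in the scenarios examined.

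Sections 1.1, 1.5 and 1.6.5 disagree on when quality of life, depression and anxiety are measured. That is a separate matter to reconcile.

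### The outcome-microbiome models may be fitted by GEE on about 30 to 36 patients, and no small-sample correction is specified

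*Combined protocol and SAP*

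**What the plan says.** Section 5.7.2 assigns methods by question. The two FMT groups are compared on HOMA-IR, weight, appetite, quality of life, anxiety and depression with generalized linear mixed models. The link between outcomes and the IM is handled separately: "The relationships between changes in outcomes and IM will first be investigated using correlation analysis". When covariates or several time points enter, the section continues: "we will employ generalized linear and nonlinear mixed models, as well as the generalized estimating equations approach". It also states that "all tests will be two-sided with a significance level of 5" per cent, and offers Holm or Benjamini-Hochberg adjustment where needed.

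On the number of independent patients, section 5.7.1 says "we plan to recruit until we have randomized 36 eligible patients" and "we assume that 15 patients per group will finish the intervention". Section 5.8.1 also gives 36, whereas section 1.1 says "We plan to randomize 30 patients". On visits, section 1.5 says "Baseline measurements will be repeated at 1 and 3 months post FMT", with some questionnaires excepted.

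The plan names SAS and R but no procedure. For GEE it gives no variance estimator, reference distribution, working correlation or small-sample correction.

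**The concern.** The usual GEE sandwich variance is justified when there are many independent clusters. Here a cluster is a patient, and there are only about 30 to 36 of them, each with two or three records. At that size the uncorrected sandwich is biased low and is itself noisy, and a normal reference ignores the noise. Both effects push p-values down. The shortfall grows when patient-level covariates are added or when the tested covariate is skewed.

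The stake is the error rate of the outcome-IM associations. The section sets a formal 5% level for all tests, and the adjustment methods it names take valid p-values as their input.

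**Working it through.** **Inputs from the documents.** Two-sided 5% level (5.7.2). 36 randomized, 18 per group, 20% attrition, 15 completers per group (5.7.1). Measurements at baseline, 1 and 3 months (1.5), so two changes or three measurements per patient.

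**Inputs assumed, because the documents give none.** Exchangeable working correlation, true within-patient correlation 0.5, normal or log-normal data, and 0, 2 or 4 extra patient-level covariates beside time and group.

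**Step 1: number of clusters.** 36 × 0.8 = 28.8, or 14.4 per group. The stated 15 per group (30 in total) is within 2 patients of this. The checks below use 30 and 36.

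**Step 2: rejection rates with no true effect.** Gaussian GEE, 3,000 runs per setting. The simulation standard error is √(p(1−p)/3000): 0.4 points at 5%, 0.55 at 10%, 0.7 at 17%. Nominal level 5%.

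| Patients | Tested term | Uncorrected sandwich, z test | Mancl-DeRouen, t on patients minus parameters |
|---|---|---|---|
| 30 | IM covariate, normal | 7.5-12.6% | 3.0-6.0% |
| 30 | IM covariate, log-normal | 13.2-17.0% | 2.9-6.1% |
| 30 | group or group-by-time | 6.1-10.1% | 2.4-5.0% |
| 36 | IM covariate, normal | 8.1-11.0% | 3.8-5.1% |
| 36 | IM covariate, log-normal | 12.7-15.9% | 2.8-6.7% |
| 36 | group or group-by-time | 5.2-9.8% | 2.8-4.6% |

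In the log-normal rows the outcome is log-normal too. The group rows pool normal and log-normal data. The rows for an IM covariate at 36 patients lack four settings (baseline IM, three visits, 2 or 4 extra covariates). The mean of the 12 normal-IM settings at 30 patients is 124.1/12 = 10.3%.

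A second simulation used five-term models with 30 or 36 patients, 2 or 3 visits and the same correlation. It gave 8.0-11.1% (normal covariate) and 14.7-17.4% (skewed) uncorrected, against 4.2-6.1% and 5.6-7.6% corrected.

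**Step 3: where the excess comes from.** Take 30 patients, two visits, a normal baseline IM covariate and two extra covariates. The average sandwich standard error is 0.873 of the true standard deviation. Bias alone would give 2 × [1 − Φ(1.96 × 0.873)] = 2 × [1 − Φ(1.711)] = 8.7%. The simulated rate is 11.2%; the rest reflects variability of the standard error. A t reference without correcting the standard error gives only 9.6%. Both changes together give 3.9%. Over all normal-IM settings at 30 patients, a t reference alone still leaves 6.2-11.1%. The variance correction is therefore the part that matters most.

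**Step 4: multiplicity adjustment.** In five-term models with 30 patients and a normal IM covariate, uncorrected p-values fall below 0.001 in 0.9-1.3% of null tests, 9 to 13 times the nominal 0.1%. As an illustration only, assume 50 independent null tests (the documents give no count), so the Bonferroni threshold is 0.05/50 = 0.001. The family-wise error would be 1 − (1 − 0.009)^50 = 36% to 1 − (1 − 0.013)^50 = 48%, against 1 − 0.999^50 = 4.9% with valid p-values.

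**The case against.** The strongest reply is that the plan never says it will use the uncorrected sandwich. That is right: it is silent, and the error depends on the choice. GEE with model-based standard errors rejected 5.5-7.6% in comparable runs (30 or 36 patients, five terms, 3,000 runs each). The result is therefore conditional. Silence nevertheless leaves the uncorrected version open to the analyst, and the stated 5% level would then be missed.

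A second reply is that the size is not a property of the plan. This also stands. One fixed doubling of the error rate is tempting, but the rate depends on the tested term, the covariates and the skewness, so it has to be given as a range. Section 5.7.3 analyses all dosed patients, so up to 36 clusters may contribute; the table shows that this changes little. Only two visits follow FMT, so three records per patient means counting baseline as a measurement; the problem appears with two records as well.

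A third reply is scope. Section 1.2 lists the IM under other measurements, section 5.7.1 calls the study a pilot, and GEE is one of two model families for a follow-up to correlations. This limits the importance, but section 5.7.2 exempts none of these tests from its 5% level. The preference for effect sizes over p-values in section 5.6.1 concerns differential abundance between groups, not these models.

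A reader might infer that the models will be run on many taxa, or that they carry a declared mechanistic aim. The supplied text states neither for GEE, and section 5.7.2 foresees dimension reduction.

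**Conclusion.** The point holds as a conditional one. Run with the standard sandwich and a normal reference on 30 to 36 patients, the GEE outcome-IM models would reject about 8-11% of true nulls for a roughly normal IM covariate. At 30 patients the full span is about 6-17%; the lowest value found at 36 was 5.2%, for a group-by-time term. These figures rest on an assumed within-patient correlation of 0.5, an exchangeable structure and 0 to 4 extra covariates. The direction is the same at 30 and 36 patients, so the conflict between sections 1.1 and 5.7.1, which needs reconciling in its own right, does not alter it.

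A reader might infer that the primary HOMA-IR test is inflated. The documents do not support that: this comparison and those of the secondary outcomes use generalized linear mixed models. Nor do these calculations show any fault in the mixed models, since none was tested.

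**What to change.** Add to section 5.7.2, for the outcome-IM models:

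> GEE analyses will use a bias-corrected sandwich variance (Mancl-DeRouen or equivalent), a t reference with degrees of freedom equal to patients minus regression parameters, and an exchangeable working correlation [or another stated structure]. Strongly skewed microbiome variables will be transformed before modelling.

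The exchangeable structure is the one simulated; what matters is that one is named in advance. A blanket Kenward-Roger rule for the mixed models should not be attached to this change: it was not examined here, and its suitability for the generalized and nonlinear mixed models in the plan is not shown.

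The cost is a sentence and an analysis option. Intervals become slightly wider. With several covariates the corrected test can be somewhat conservative (down to about 3% for an IM term at 30 patients). If covariates stay strongly skewed, rejection of about 6-8% may remain, which is the reason for transforming first.
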